5.8 Interruption of Enrollment/Trial Cessation

This section lists clinical and laboratory adverse events that will necessitate interruption of enrollment in the trial as a whole. As part of their ongoing safety review, the DSMB will make independent judgments regarding other adverse events requiring trial interruption. In addition, should the study be stopped, the FDA will be informed and the study will not resume until both the DSMB and the FDA are in agreement.

1. Any drug related death or Grade 4 SAE; During this trial, any grade 4 SAE death event will be temporarily considered unexpected and potentially drug-related until the event is reported and reviewed by the FDA and DSMB. In this event, the trial will be interrupted, including dosing of participants already enrolled and enrollment of new participants, until the grade 4 SAE or death event is reviewed by both the FDA and DSMB and both agree to the restart of trial enrollment and study agent administration.
2. Severe adverse event (defined in section 7.3) that is possibly, probably or definitely related to study treatment in any of the first 3 participants, or severe adverse events in the same organ system in any 2 participants with the exception of Grade 3 lymphopenia within the first 30 days of drug treatment. This criterion supersedes all rules below (3-8).
3. Occurrence of anaphylaxis during study treatment in any participant. Anaphylaxis is a serious allergic reaction that is rapid in onset and may cause death. Anaphylaxis is highly likely when any one of the following 3 criteria are fulfilled:
 1. Acute onset of an illness (minutes to several hours) with involvement of the skin, mucosal tissue, or both (e.g., generalized hives, pruritus or flushing, swollen lips-tongue-uvula)

AND AT LEAST ONE OF THE FOLLOWING:

 - i. Respiratory compromise (e.g., dyspnea, wheeze-bronchospasm, stridor, reduced peak expiratory flow (PEF), hypoxemia)
 - ii. Reduced Blood Pressure (BP) or associated symptoms of end-organ dysfunction (e.g., hypotonia [collapse], syncope, incontinence)
 2. Two or more of the following that occur rapidly after exposure to a likely allergen for that person (minutes to several hours):
 1. Involvement of the skin-mucosal tissue (e.g., generalized hives, itch-flush, swollen lips-tongue-uvula)
 2. Respiratory compromise (e.g., dyspnea, wheeze-bronchospasm, stridor, reduced PEF, hypoxemia)
 3. Reduced BP or associated symptoms (e.g., hypotonia [collapse], syncope, incontinence)

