7.3 Serious Adverse Event/Reaction

A serious adverse event (SAE) or reaction is defined as “any adverse event occurring at any dose that suggests a significant hazard, contraindication, side effect, or precaution.” An adverse event

or suspected adverse reaction is considered “serious” if, in the view of either the investigator or sponsor, it results in any of the following outcomes:

1. Death. A death that occurs during the study or that comes to the attention of the investigator during the protocol-defined follow-up after the completion of therapy must be reported whether it is considered to be treatment related or not.
2. A life-threatening adverse event. The term life-threatening is defined as (1) diseases or conditions where the likelihood of death is high unless the course of the disease is interrupted and (2) diseases or conditions with potentially fatal outcomes, where the endpoint of clinical trial analysis is survival (21 CFR 312.81(a)).
3. Inpatient hospitalization or prolongation of existing hospitalization with the exception of hospitalization relating to initial diagnosis of stage 3 type 1 diabetes. Symptoms/reactions of stage 3 T1D onset which require intravenous intervention for diabetes management in an emergency room, physician’s office or visiting nurse.
4. Persistent or significant incapacity or substantial disruption of the ability to conduct normal life functions
5. Congenital anomaly or birth defect.
6. Important medical events that may not result in death, be life-threatening, or require hospitalization may be considered serious when, based upon appropriate medical judgment, they may jeopardize the participant and may require medical or surgical intervention to prevent one of the outcomes listed above.

Adverse event or suspected adverse reaction are considered “life-threatening” if they are (1) diseases or conditions where the likelihood of death is high unless the course of the disease is interrupted and (2) diseases or conditions with potentially fatal outcomes, where the endpoint of clinical trial analysis is survival (21 CFR 312.81(a)).

Regardless of the relationship of the adverse event to study drug, the event must be reported as a serious adverse event if it meets any of the above definitions.

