7.6 Grading Event Severity and Causality

TrialNet has adopted usage of the National Cancer Institute (NCI) Common Technology Criteria for Adverse Events (CTCAE) and/or study-specific criteria for classification to describe the severity of adverse events with the exception of severe hypoglycemia and hyperglycemia. Hypoglycemia and hyperglycemia will be reported as adverse events only in the case of requiring the assistance of others due to loss of consciousness or diabetic ketoacidosis. TrialNet Investigators will also provide an assessment of relationship of AE to study drug as not, unlikely, possibly, probably, or definitely related.

The reference safety information to be used by the TrialNet Investigators for evaluation of expectedness of adverse events shall be the adverse reaction section of the current approved product label available in the country.

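### SAE item 3 can be read two ways for Stage 3 onset treated intravenously without admission, so part of the primary endpoint may enter SAE counts by arm

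*Combined protocol and SAP*

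**What the plan says.** Section 7.3 lists the outcomes that make an event serious. Item 3 reads "Inpatient hospitalization or prolongation of existing hospitalization with the exception of hospitalization relating to initial diagnosis of stage 3 type 1 diabetes". After a full stop comes a second sentence with no main verb: "Symptoms/reactions of stage 3 T1D onset which require intravenous intervention for diabetes management in an emergency room", or in a physician's office or by a visiting nurse.

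Three other provisions bear on the same event:

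- Item 2 ("A life-threatening adverse event. The term life-threatening is defined as" and so on) and item 6 (important medical events) carry no Stage 3 exemption. The section closes by saying that, whatever its relationship to study drug, "the event must be reported as a serious adverse event if it meets any of the above definitions".
- Section 7.6 says that hypoglycemia and hyperglycemia are "reported as adverse events only in the case of requiring the assistance of others due to loss of consciousness or diabetic ketoacidosis".
- Section 5.8, halting rule 2, uses the term severe adverse event and defines it by pointing to section 7.3.

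SAE status triggers 24-hour reporting to the coordinating center, DSMB review, and notice to the drug supplier within one business day regardless of causality (section 7.7).

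**The concern.** The second sentence of item 3 stands inside a list of serious outcomes, so on its face it is one more criterion. It also follows directly on an exception for Stage 3 onset and may have been meant to extend it. The protocol does not say which. Two sites following the text in good faith could classify the same event in opposite ways.

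The event concerned is the onset of Stage 3, the primary endpoint. If ATG works, onset is rarer per participant on ATG. Any part of onset that is coded as serious then lowers the ATG SAE rate relative to placebo for a reason unrelated to safety, and could partly hide real toxicity. If ATG sped up progression, a possibility that section 6.2.1 acknowledges, the distortion would run the other way. How much of onset is counted would depend on local admission practice and on how each site reads the sentence.

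**Working it through.** **Setting the provisions side by side.** The plan states no figure on this point, so there is none to reproduce. Four kinds of onset show the effect of each reading.

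| Onset event | Fragment read as a criterion | Fragment read as part of the exception |
|---|---|---|
| Admitted, not life-threatening | Not an SAE under item 3; item 6 may apply | Same |
| Admitted, life-threatening | Excepted in item 3, SAE under item 2 | Same |
| Intravenous treatment, ketoacidosis, not admitted | SAE under item 3 | Not under item 3; items 2 or 6 may apply |
| Intravenous treatment, no ketoacidosis or loss of consciousness, not admitted | SAE under 7.3, yet not a reportable AE under 7.6 | Not under item 3; not a reportable AE under 7.6 |

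Only the last two rows change with the reading. On the literal reading, rows 1 and 3 also differ from each other by care setting.

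**Inputs for the size.** From section 8.4: 24-month placebo risk 50%, hazard ratio 0.4, allocation 68 to 33. Assumed, because the documents give no figure: a share f of 5%, 10% or 25% of onsets needs intravenous care, equal in both arms. Also assumed: proportional hazards and no dropout.

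**Onset risk on ATG.** 1 − 0.5^0.4 = 1 − 0.758 = 0.242. The ratio is 0.242 / 0.50 = 0.48, and f cancels out of it.

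**Addition to SAE rates at 24 months** (risk × f, per 100 participants). The last two columns add an assumed 5% risk s of other SAEs, equal in both arms, using 1 − (1 − s)(1 − f × risk).

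| f | Placebo, onset only | ATG, onset only | Placebo, with 5% other | ATG, with 5% other |
|---|---|---|---|---|
| 5% | 2.5 | 1.2 | 7.4 | 6.2 |
| 10% | 5.0 | 2.4 | 9.8 | 7.3 |
| 25% | 12.5 | 6.1 | 16.9 | 10.8 |

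With no true difference in other SAEs, the overall ATG/placebo ratio becomes about 0.83, 0.75 and 0.64.

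These are upper bounds for the ambiguity. They apply f to all onsets needing intravenous care, and only those treated without admission change with the reading.

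**Counts.** Expected onsets by 24 months are 33 × 0.50 = 16.5 on placebo and 68 × 0.242 = 16.5 on ATG. The number of onset SAEs would therefore look balanced between arms while the rates differ about twofold.

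**Halting rule 2.** Its second limb concerns events of one organ system in two participants. It does not repeat the relatedness condition, and it is unclear whether the 30-day limit governs the whole limb or only the lymphopenia exception. Over 24 months the expected onset SAEs in both arms together are f × 33 = 1.7, 3.3 or 8.3. Within 30 days the onset risks are 1 − 0.5^(30/730.5) = 2.8% on placebo and 1 − 0.5^(0.4 × 30/730.5) = 1.1% on ATG. That is about 0.9 + 0.8 = 1.7 onsets, and f times this is about 0.1 to 0.4 SAEs. The reading of item 3 matters for rule 2 mainly if the 30-day limit does not govern that limb.

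**The case against.** The strongest reply is that this is a punctuation slip. If the fragment continues the exception, nothing enters SAE counts through it. That is a possible reading, and it is why the certain defect is ambiguity. The text still does not select it, and the fragment's place in a list of serious outcomes favors the other.

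A reader might go further than the documents allow in four ways.

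- *That the plan counts the milder onset and leaves out the graver one.* This follows on the literal reading only, and under item 3 only. An admitted onset can still be an SAE through items 2 or 6, and a life-threatening one is.
- *That a planned SAE comparison is biased.* No formal one is planned. Section 8.2 applies Fisher's exact test to grade 3 or higher events and specific toxicities, descriptively and with nominal p-values.
- *That halting rule 1 is affected, since "any grade 4 SAE death event will be temporarily considered unexpected and potentially drug-related".* This adds little. Section 7.7 describes grade 4 as life-threatening or disabling, and such events are largely SAEs through items 2 or 4 however item 3 is read.
- *That the size can be scaled against the four SAEs in the 29 ATG-only participants of TN19.* Those participants already had Stage 3 disease at entry, so none of those events could be an onset event.

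Two further replies have weight. Section 7.6 can be taken to settle the fourth row of the table, because an event that is not a reportable AE is arguably not an SAE; but no order of precedence is stated. A high share is also unlikely if participation reduces ketoacidosis at onset in children, as section 2.4 says, and scheduled OGTTs and three-monthly calls point the same way. The DSMB is also told of progressions as they occur (section 8.5.1), so it could identify onset SAEs if they were marked as such.

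**Conclusion.** The concern holds as an ambiguity with consequences for safety reporting. Item 3 does not settle whether an onset treated intravenously without admission is an SAE. On the literal reading, status under item 3 turns on care setting, and 7.3 conflicts with 7.6.

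The ATG/placebo ratio of about 0.48 for the onset component rests on the design hazard ratio, the 50% placebo risk and an equal share in each arm. The absolute size rests on a share that the documents do not give, so the 5% to 25% range shows scale and is not an estimate. If the fragment belongs to the exception, the contribution through it is zero.

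What is exposed is SAE reporting, DSMB review of SAEs, and possibly halting rule 2. The primary analysis and its error rate are untouched. This should be corrected but does not threaten the trial's main conclusion.

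**What to change.** Rewrite item 3 as one complete rule under which the SAE status of onset-related acute care does not depend on where it was given. State how that rule stands against items 2 and 6, and reconcile it with section 7.6 and the halting rules in section 5.8, including what rule 2 takes from section 7.3 and which part of it the 30-day limit governs. Which status is right is for the sponsor to decide, and nothing here argues for either.

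Whatever status is chosen, show onset-related SAEs as a separate line by arm, with denominators, in DSMB and final safety tables, so that SAE summaries can be read with and without them.

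The cost is one clarifying protocol paragraph and one extra table, with no new data collection. It is best done before sites begin to code onsets differently.

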7.4 Adverse Events of Special Interest

An adverse event of special interest (AESI) can be serious or non-serious but is one of concern specific to the sponsor’s product. Adverse events categorized as such require ongoing monitoring and rapid communication by the investigator to the sponsor. AESIs grade 1 or higher will be reported electronically to the TNCC. The DSMB and the FDA will be notified of Grade 3 or greater or hospitalization events in relation to Serum Sickness. AESI include the following conditions/symptoms:

- Anaphylaxis
- Cytokine Release Syndrome
- Hematologic Effects (i.e. lymphopenia, Neutropenia, thrombocytopenia)
- Serum Sickness
- Infections
-

7.5 Unexpected Adverse Event

An adverse event/reaction is considered unexpected when the nature (specificity) or severity of the event is not consistent with the risks described in the Investigator's Brochure or the informed consent document. Unexpected refers to an experience that has not been previously observed. This includes events that occur more frequently than expected.

7.6 Grading Event Severity and Causality

TrialNet has adopted usage of the National Cancer Institute (NCI) Common Technology Criteria for Adverse Events (CTCAE) and/or study-specific criteria for classification to describe the severity of adverse events with the exception of severe hypoglycemia and hyperglycemia. Hypoglycemia and hyperglycemia will be reported as adverse events only in the case of requiring the assistance of others due to loss of consciousness or diabetic ketoacidosis. TrialNet Investigators will also provide an assessment of relationship of AE to study drug as not, unlikely, possibly, probably, or definitely related.

The reference safety information to be used by the TrialNet Investigators for evaluation of expectedness of adverse events shall be the adverse reaction section of the current approved product label available in the country.

7.7 Adverse Event Reporting and Monitoring

The investigator will grade their severity according to common toxicity criteria or study-specific criteria and will decide of their relation to therapy. Events will be assessed and reported consistent with the ICH Guidelines for Good Clinical Practice, 21 CFR 312.32 for expedited safety reporting, and per the guidance of the DHHS Office for Human Research Protections (OHRP). General descriptions of grading are as follows:

- Grade 1 are mild adverse events requiring no specific medical intervention or asymptomatic laboratory findings
- Grade 2 are moderate adverse events, minimal, local, non-invasive intervention
- Grade 3 are severe and undesirable events, significant symptoms requiring hospitalization or invasive intervention
- Grade 4 are life-threatening or disabling events
- Grade 5 are fatal events (death)

The adverse event case report form for the protocol must be completed for all adverse events assessed as grade 2 or higher and grade 1 and higher for AESIs. The investigator is responsible for regular participant follow-up and for ensuring all adverse events are documented and reported appropriately. For reporting serious adverse events (SAE), in addition to the AE case report form, the site should also complete a MedWatch Form and email/fax to the TNCC *within 24 hours of when the site is notified of the event*. This will be reviewed by the TrialNet Medical Monitor and the DSMB as appropriate. Death must be reported immediately. Event outcome and other follow-up information regarding the treatment and resolution of the event will be obtained and reported when available, if not known at the time the event is initially reported. The follow-up information should

contain sufficient detail to allow for a complete medical assessment of the case and an independent determination of possible causality.

Data will be submitted to the TNCC and be kept by TNCC in keeping with all applicable agreements and when requested, such as for periodic safety assessments, review of IND annual reports, review of IND safety reports, and preparation of final study reports. The investigators will ensure prompt reporting of all events to the TNCC who will facilitate the required safety reporting to any oversight bodies as applicable (e.g., Medical Monitor, DSMB, cIRB, sponsor). The investigator must continue to follow the participant until the AE has subsided or until the condition becomes chronic in nature, stabilizes (in the case of persistent impairment), or the participant dies. Upon the receipt of follow-up information, the investigator must update the AE case report form and the MedWatch Form, if applicable.

Unless otherwise specified, all SAEs (regardless of relationship to the investigational agents) must be reported to the TNCC no later than 24 hours of learning of the event. The Medical Monitor's assessment and determination of the nature of the SAE (seriousness, expectedness, relatedness) and determination of expedited reporting mechanism (e.g. for SUSAR) to the FDA will be kept at TNCC as part the of safety monitoring record. The TNCC is responsible for immediately notifying the sponsor when a SUSAR is identified in order to comply with FDA reporting requirements. Any additional follow-up information obtained from the site after the initial report should be submitted to the TNCC via an updated MedWatch form as applicable. The TNCC will ensure the sponsor is notified of any follow-up MedWatch forms received in compliance with all reporting guidelines.

Adverse events will be assessed by the TrialNet Medical Monitor. The DSMB will conduct regular safety reviews approximately every three to six months (and otherwise as needed) of adverse events by treatment group assignment. Serious adverse events as well as adverse events leading to study discontinuation will be reviewed by the DSMB.

For SAEs that are unexpected and considered possibly or probably drug related, the TNCC can provide information on frequency of similar events, and generate FDA form 3500A reports (MedWatch form) for distribution to FDA, NIDDK, DSMB and site investigators. Expedited safety reports will be submitted to the FDA by the sponsor, NIDDK per the required reporting timelines. The TNCC will also be primarily responsible for sending required safety information to Sanofi.

TrialNet will inform Sanofi of all SAEs and Adverse Events of Special Interest (AESIs) regardless of Investigator's causality within 1 business day.

8 STATISTICAL CONSIDERATIONS AND ANALYSIS PLAN

Analyses of study data will be conducted to address all objectives of the trial and other interrelationships among data elements of interest to the investigators and of relevance to the objectives of the study. Analyses by gender and race/ethnicity, as appropriate, are also planned.

Primary analysis of treatment effect will be conducted under the intention-to-treat principle whereby outcome data from all participants randomized will be included regardless of treatment compliance.

8.1 Primary Outcome and Analyses

The primary outcome is the elapsed time from random treatment assignment to the development of diabetes or time of last contact among those randomized.

Criteria for stage 3 diabetes onset are, as defined by the American Diabetes Association (ADA), based on glucose testing, or the presence of unequivocal hyperglycemia with acute metabolic decompensation (diabetic ketoacidosis) as defined below:

1. Unequivocally symptomatic* AND at least one of the following:

1. Random glucose ≥ 200 mg/dl [11.1 mmol/L] OR
2. Fasting glucose ≥ 126 mg/dl [7 mmol/L] OR
3. OGTT = diabetic OR
4. HbA1c $\geq 6.5\%$

* Unequivocal symptoms: severe/persistent polyuria, polydipsia and/or significant unexplained weight loss

2. If not unequivocally symptomatic, two separate objective measures are required for diagnosis. These tests must occur at least one day apart but as soon as possible and must be consecutive, defined as without an intervening non-diabetic OGTT.

1. The preferred object measures for diagnosis are:

1. 2 diabetic OGTTs, not on the same day (the confirmatory OGTT is the date of diagnosis)
2. However, if an individual is diagnosed without the consecutive OGTTs, the following also constitutes diagnosis in TrialNet:
 1. Diabetic OGTT + FPG ≥ 126 mg/dl [7 mmol/L] not on the same day
 2. Diabetic OGTT + HbA1c $\geq 6.5\%$ (these may be on the same day)
 3. FPG ≥ 126 mg/dl [7 mmol/L] + HbA1c $\geq 6.5\%$ (these may be on the same day)

It is preferred that OGTTs for Stage 3 T1D diagnosis are analyzed using TrialNet laboratories. If a participant has an OGTT that indicates diabetes (clinical alert), the site should invite the participant for a repeat OGTT as soon as possible. To make a diagnosis of Stage 3 T1D diabetes, each of two consecutive OGTTs must meet diabetes criteria. Thus, if the second OGTT does not confirm the diagnosis, the participant will continue to be followed in the ATG Low-Dose Prevention Study and will be asked to return for the next follow-up visit. At that time, the OGTT will be repeated and, if indicative of diabetes, will need to be performed a second time to confirm the diagnosis.

In the case of symptoms or unequivocal hyperglycemia with acute metabolic decompensation (diabetic ketoacidosis), repeat testing is not required to confirm the diagnosis of Stage 3 T1D and prompt evaluation and initiation of clinically indicated treatment will occur.

The TrialNet Eligibility and Events Committee will review and adjudicate any cases with only a single objective measure, cases which do not meet the criteria above, and/or cases which have uncertain results of tests and/or the test procedures. Qualifying glucose values should be from laboratory tests, rather than capillary blood glucose meter readings.

The study design is a 2:1 randomized, double-blind placebo-controlled trial. The primary objective of this trial is to assess the efficacy of ATG versus placebo control in terms of the risk of diabetes onset in this target population as defined by the eligibility criteria.

The cumulative incidence of diabetes onset over time since randomization within each treatment group will be estimated using the Kaplan-Meier method (proportion surviving diabetes-free as a function of time). The difference between groups in the cumulative incidence functions, and the associated hazard functions, will be tested at the 0.05 level, two-sided, using the Cox Proportional Hazards (PH) model, adjusted for age. Assumptions of proportionality will be tested, and if that assumption does not hold, then alternative analytic approaches will be used to allow for time-varying coefficients in the model. The relative risk of diabetes onset between groups will be estimated from the Cox regression model. The critical values will be determined by the group-sequential procedure outlined in the section entitled Interim Monitoring Plan below.

